7.1. Study Treatment Doses and Regimens

The study is divided into 2 parts; Part 1 (Cohorts 1-8) is considered the FIH, single ascending dose phase of the study, where subjects will receive a single oral fasted dose, and which includes different formulations to allow assessment of relative bioavailability. Subjects will be randomized to the following treatments:

Emodepside Liquid Service Formulation (LSF) solution (concentration of 1 mg/mL) or matching placebo solution for Cohorts 1, 2, 3, 5, 6 and 8; emodepside immediate release (IR) tablets of 5 and 20 mg or matching placebo tablets for Cohorts 4 and 7, respectively.

Part 2 is considered exploratory and will involve doses already tested. Therefore it is not considered to be FIH. The planned doses for Part 2 are 10 mg LSF solution or matching placebo solution in the fed state for Cohort 9 and 40 mg LSF solution or matching placebo solution (fasted) in Cohort 10.

The planned and actual treatments administered are described below in Table 6.

7.2. Allocation to Treatment

Randomised Subjects will be given a unique ID (subject number; Table 6) that will be recorded in the case report form (CRF), and will be retained throughout the study. This subject number will also appear on the study medication containers.

Table 6. Study Treatment: Subject Numbers, Formulation, and Dose-Levels by Cohort

Cohort	Subject	Dose Level of	Formulation and Route of	Planned Subjects				
	Numbers ^a	Study Treatment	Administration	Emodepside	Matching Placebo			
Part 1*								
Cohort 1	1001 - 1008	1.0 mg	LSF solution, p.o.	6	2			
Cohort 2	2001 - 2008	2.5 mg	LSF solution, p.o.	6	2			
Cohort 3	3001 - 3008	5.0 mg	LSF solution, p.o.	6	2			
Cohort 4	4001 - 4008	5.0 mg	IR tablet, p.o.	6	2			
Cohort 5	5001 - 5008	10.0 mg	LSF solution, p.o.	6	2			
Cohort 6	6001 - 6008	20.0 mg	LSF solution, p.o.	6	2			
Cohort 7	7001 - 7008	20.0 mg	IR tablet, p.o.	6	2			
Cohort 8	8001 - 8008	40.0 mg	LSF solution, p.o.	6	2			
Part 2**								
Cohort 9	9001 - 9008	10.0 mg	LSF solution, p.o.	6	2			
Cohort 10	9501 - 9508	40.0 mg	LSF solution, p.o.	6	2			

^{*}Part 1 is the FIH, SAD part of the study.

The first two subjects in Cohort 1 (subjects 1001 and 1002), will be the leading subjects. The Investigator will review all safety and tolerability data (including laboratory safety tests) up to 23 h after dosing of leading subjects before dosing the remaining subjects in the cohort.

^{**}Part 2 is the exploratory phase (including Cohorts 9 and 10).

^a Any subjects who are replaced in a cohort will have the subject number incremented by 100 (eg, 1001 would be replaced by 1101)

7.3. Drug Supplies

Formulation and Supplier: Emodepside will be supplied by the Sponsor, DNDi, as emodepside LSF solution and tablets, each with matching placebo.

The study drug will be delivered by the sponsor to the study site in bulk. It will be the responsibility of a relevant member of the pharmacy/pharmacy delegate to prepare the individual treatments.

Labelling, Packaging: Emodepside supplied by the Sponsor will be manufactured, packed, labeled and shipped according to the current GMP guidelines and local legal rules. Bulk-supplies of emodepside will be delivered to the pharmacy of the Phase 1 Unit.

A relevant member of the pharmacy/pharmacy delegate will dispense study drugs as individual doses for each subject according to the Pharmacy Manual.

Preparation and Dispensing: Emodepside LSF solution and tablets will be dispensed in the Phase 1 Unit to the individual dosing containers by 2 appropriately qualified members of the pharmacy team. Instructions provided in the Pharmacy Manual/Study Procedures Manual must also be followed.

Administration: Following a fast overnight (of not less than 9 hours; fasted subjects) or an FDA breakfast (fed subjects), investigator site personnel will administer study medication to subjects on Day 0, with ambient temperature water to a total volume of approximately 240 mL.

Subjects will swallow the study medication whole, for doses of tablets, the subject will not chew the medication prior to swallowing. All subjects will be required to refrain from drinking beverages other than water during the first 4 hours after dosing. Subjects will not eat until at least 4 hours after dosing, and not until all study assessments scheduled for that time have been completed. Instructions provided in Section 4.3. and the Study Procedures Manual regarding meals must also be followed.

Compliance: Study treatment will be administered under the supervision of investigator site personnel, who will monitor the subjects according to their standard procedures to ensure treatment compliance.

7.4. Dose Escalation and Stopping Rules

During the study, the dose will be increased only if the safety and tolerability and, from Cohort 3 onwards, the PK of the previous dose is acceptable.

Planned dose levels may be changed based on emerging data. The top planned dose for the IR tablet is 20 mg and for the LSF solution is 40 mg.

The first fed dose will not exceed half the highest dose, of the same formulation, that has previously been shown to cause no safety concerns in the fasted state.

Decisions about dose escalation will be made by the participants in the Safety Review Meeting (SRG; see Section 11 on Safety Review Meetings). The dose will not be increased until the SRG have reviewed safety and tolerability data, up to a

minimum of 96 h after dosing and, from Cohort 3 onwards, a minimum of 24 h post-dose preliminary PK data from the highest dose level tested to date. The data reviewed by the SRG will be from at least 6 subjects in a Cohort (at least 4 subjects of whom have completed active treatment).

If, within a treatment group, any of the following occurs, dose escalation will be stopped:

Safety stopping criteria

- There is 1 or more serious adverse event, considered to be related to emodepside:
- 2 or more subjects who present any severe adverse event considered to be related to emodepside

If a cohort fulfils a dose escalation stopping criterion, that dose level will not be repeated.

PK stopping criteria

 predicted mean plasma concentrations in the subjects at the next scheduled dose level exceed or equal: C_{max} 634 μg/L, AUC₍₀₋₂₄₎ 6025 μg·h/L (based on the NOAEL level in dog toxicology studies, exposures resulting from 4 weeks of treatment at 10 mg/kg/d)

The scheduled dose of emodepside may be reduced if, for example, the results of safety tests give any cause for concern, or tolerability is poor.

If adverse events occur that cause mild or moderate discomfort but do not in any way threaten the health of the subject, that dose level may be repeated with the aim of exploring further the relationship between dose and adverse event. If, in the judgement of the SRG, it would not be reasonable to expose further subjects to the level of discomfort experienced by the subjects who have already received the dose, the next scheduled dose may be reduced. The reduction may be either to one of the dose levels that has already been given, or to an intermediate level that has not previously been given; in either case, the aim is to learn more about the relationship between adverse event and dose (or plasma concentration) of drug.

Optionally, if further information is required to guide dose escalation decisions, an independent advisor(s) may be consulted, who will have access to unblinded data (see Section 11, Safety Review Meetings).

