Subjects may withdraw from the study at any time at their own request, or they may be withdrawn at any time at the discretion of the investigator or sponsor for safety, behavioral, or administrative reasons.

Subjects who withdraw, or are withdrawn from the study may be replaced at the discretion of the investigator upon consultation with the sponsor.

Safety Review

Safety will be reviewed throughout the study in Safety Review Meetings. Participants in the Safety Review Meeting will be at a minimum the Principal Investigator or his/her deputy and at least one Sponsor's representative (medically qualified). As an option, independent advisor(s) will be appointed, who will have access to unblinded data to advise if required (eg, on dose escalation decisions.)

Study Duration

Subject participation in the study will be for up to 7 weeks, including a screening phase (within 4 weeks prior to dosing), an in-house 1–week evaluation phase (Day -2 to Day 7), that will be followed by discharge on Day 7 for Options 1 and 2; with ambulatory evaluation visits scheduled as needed for Option 2 (up to maximally the follow-up visit on Day 21), or by a prolonged in-house evaluation phase (up to maximally Day 14) for Option 3, and a follow-up visit 3 weeks (+3 days) after dosing.

Rationale for Dose Selection and Route of

Rationale for Starting Dose

The recommended starting dose in humans (70 kg) was calculated to be 1.75 mg/day (0.025 mg/kg), based on the following data:

Administration

28 days rats study: No Observed Adverse Effect Level (NOAEL) = 5 mg/kg ► Human Equivalent Dose (HED)+ safety factor 10 = 0.082 mg/kg

28 days dog study: NOAEL = 5 mg/kg ► HED + safety factor 10 = 0.27 mg/kg

Dosages resulting in Margins of Safety of 10 from predicted human PK (unbound Cmax from dog scenario):

- 28 days rats study: NOAEL = 5 mg/kg ▶ 0.048 mg/kg
- 28 days dog study: NOAEL = 5 mg/kg ▶ 0.075 mg/kg
- Single administration rat: NOAEL = 10 mg/kg ▶ 0.035 mg/kg

1.75mg is not practical to dose in the Liquid Service Formulation (LSF, solution), and it is not recommended to dose the LSF in less than 0.5mL (0.5mg) increments. 1mg is chosen as the starting dose. Two dose steps are required to reach the 5mg dose (tablet).

Rationale for Study Population

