1.2. Summary of Non-Clinical Information

An extended battery of nonclinical studies supported the marketing of emodepside as a veterinary drug. To support the clinical development of emodepside in healthy volunteers and patients suffering from river blindness, additional studies have been performed to ensure all requirements for administration in man are met.

Pharmacology

A surrogate filarial nematode species was used (*Litomosoides sigmodontis*) which represents a permissive disease model considered to be a reasonable predictor for *Onchocerca volvulus* infection. A comprehensive set of primary pharmacodynamic studies was performed to characterize and assess the efficacy of emodepside against different filarial nematode species. Emodepside was capable of reducing the motility of both adult worms and microfilariae in *L. sigmodontis* in vitro with a minimum inhibitory concentration (MIC) close to 0.1 µM (111.9 ng/mL). The MIC is defined as the minimum concentration inhibiting the worm's motility completely. *In vivo* Balb/c mice and jirds, a well-established, anthelmintic rodent model, were naturally infected with *L. sigmodontis* and treated with emodepside at different doses and formulations. In these studies treatment with emodepside efficiently and dose dependently reduced number of adult parasites.

A large number of safety pharmacology studies were performed in vitro (+ mechanistic studies) and in vivo in rats and dogs. In addition, standard safety pharmacology parameters were included in the toxicity studies with emodepside in rats and dogs.

Secondary pharmacology studies did not detect any off-target receptor binding at clinically relevant concentrations. The in vitro hERG assay showed no critical potential for QT prolongation (IC20 19 μ M).

Safety pharmacology and repeated dose toxicity studies revealed the central nervous system as a target organ with changes in behavior, activity, tremor and gait abnormalities in rats, mice and dogs. A No Observed Adverse Effect Level (NOAEL) of 5 mg/kg i.d. was defined in dogs and rats after repeated administration (4-week repeat oral dose toxicity study). 10 mg/kg body weight was established as NOEL for effects on the nervous system in fasted rats after acute administration.

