The studies in rats revealed toxicities resulting from metabolic changes induced by emodepside indirectly, such as a decrement in bodyweight gain but in parallel an increased feed and water consumption as well as deformation of teeth as a sign of a diabetic-like effect. The main affected organs were kidney, pancreas and liver, with associated changes in hematological parameters, triglyceride and glucose levels in the plasma and lipid and glycogen stores. These toxicological findings pointed to a diabetes-related condition (inhibition insulin secretion followed by increased glucose levels, reduced leptin levels, as confirmed by mechanistic studies). In mice, the NOAEL after 14 week of treatment was 50 ppm (10.5-16.8 mg/kg bw.). The NOAEL in the 14 week rat study was defined at 10 ppm (m: 0.73, f: 1.11 mg/kg bw per day); In 4-week rat studies 50 ppm (equals 4 – 5 mg/kg bw) was defined as NOAEL.

In dogs, doses starting from 10 mg/kg bw per day for 4 weeks resulted in clinical signs like vomiting, tremor and unsteady gait. At 20 mg/kg bw, an effect on nutritional state, food intake and bodyweight gain was noted. All effects were reversible after a recovery period of 4 weeks. The NOAEL for this study was 5 mg/kg bw.

Several reproductive and developmental toxicity studies were conducted in rats and rabbits. Effects of emodepside on the reproductive performance in rats occurred only at parentally toxic doses. No primary effect on fertility and reproduction was observed. In this species, both ovarian weight and gestation rate were unaffected by treatment. Primary systemic parental effects were due to diabetes I like effects, which were well known from repeat dose studies in rats. A battery of well-conducted, GLP-compliant teratogenicity studies revealed maternal toxicity, foetotoxicity, foetal malformations and various skeletal/visceral anomalies or deviations. Clinical signs of systemic maternal toxicity were evident at dose rates ≥6 mg/kg bw. Overall, severe maternal toxicity at 18 mg/kg bw resulted in adverse effects on foetal development. The NOAEL for maternal toxicity in rats was 2 mg/kg bw and the NOAEL for developmental toxicity was 0.5 mg/kg bw. However, as discussed above, diabetes like effects, which were not measured in developmental toxicity studies, occurred in lower dosages. Therefore, it can be assumed that the maternal toxic dose was

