Emodepside is registered as veterinary product worldwide. Therefore, a complete toxicological package is available which also covers human requirements.

It is shown in a set of genotoxicity studies that emodepside is not genotoxic. Additionally, developmental toxicity studies in rats and rabbits showed that emodepside had no teratogenic or primary embryo/ fetotoxic potential. However, contraception will be used during the study in accordance with MHRA request and HMR standard procedures (see Section 4.3 on Dietary and Lifestyle Guidelines).

Based on the nonclinical safety data, the toxicological release conference gave the following recommendations for the first in men study:

The recommended starting dose in humans (70kg) is 1.75 mg/day.

- Monitoring of standard parameters, including blood pressure, glucose homeostasis (glucose, insulin, glucagon). Increased glucose levels and decreased insulin and glucagon levels have been observed in the non-clinical safety studies.
- Once the dose escalation is approaching plasma concentrations which were pre-clinically associated with CNS effects, particular attention should be given to observations/investigations indicating prodromal signs of tremor and incoordination.
- Due to missing data on phototoxicity clinical trial participants should avoid exposure to excessive sunlight
- Strong CYP3A4 inducers and inhibitors as well as co-medications that are relevant substrates for CYP3A4 should be excluded or closely monitored until the drug-interaction potential has been assessed in more detail.
- Strong P-gp inhibitors as well as co-medications that are relevant substrates for P-gp should be excluded or closely monitored until the drug-interaction potential has been assessed in more detail.
- The potential of emodepside to inhibit CYP3A4 and P-gp has to be further assessed clinically once it becomes clearer which emodepside exposure will be achieved at the therapeutic dose in humans.

The NOAEL of emodepside in dogs was $AUC_{(0-24)}$ 860 μ g·h/L, C_{max} 175 μ g/L, after 1 week at a dose level of 5 mg/kg. This dose resulted in an exposure after 4 weeks of $AUC_{(0-24)}$ 1611 μ g•h/L, C_{max} 238 μ g/L.

The maximal dose tested in dogs was 20 mg/kg. This dose resulted in an exposure after 4 weeks of AUC₍₀₋₂₄₎ 15887 μg•h/L, C_{max} 1682 μg/L.

(Note: The recommended starting dose in humans (70kg) is 1.75 mg/day, however for technical reasons (see Section 3.3) the dose of 1.0 mg is chosen as the starting dose)

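### Section 7.4 labels the PK stopping limits as dog NOAEL exposures at 10 mg/kg/d, but the rest of the protocol puts the repeat-dose dog NOAEL at 5 mg/kg

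*Protocol*

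**What the plan says.** The PK stopping criterion in Protocol Section 7.4 applies when "predicted mean plasma concentrations in the subjects at the next scheduled dose level exceed or equal" Cmax 634 µg/L, AUC(0-24) 6025 µg·h/L. It gives the origin of these figures as "based on the NOAEL level in dog toxicology studies, exposures resulting from 4 weeks of treatment at 10 mg/kg/d".

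Elsewhere the protocol describes the dog data differently:

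- **Section 1.2, Toxicology:** "In dogs, doses starting from 10 mg/kg bw per day for 4 weeks resulted in clinical signs like vomiting, tremor and unsteady gait". On the same study it concludes: "The NOAEL for this study was 5 mg/kg bw".
- **Section 1.2, Pharmacology:** the 4-week repeat-dose NOAEL is 5 mg/kg in both dogs and rats.
- **Protocol Summary (starting-dose rationale) and Section 3.3:** "28 days dog study: NOAEL = 5 mg/kg". It is used for the human equivalent dose and again for the margin of safety.
- **Section 1.4:** the dog NOAEL is tied to 5 mg/kg, with exposures after 1 week (Cmax 175 µg/L, AUC(0-24) 860 µg·h/L) and after 4 weeks (238 and 1611). The 4-week exposure at 20 mg/kg is 1682 and 15887.

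No section reports the dog exposure at 10 mg/kg, and none explains the move from 5 to 10 mg/kg.

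**The concern.** These two values are the only numerical exposure limits in the stopping rules; the safety criteria beside them count adverse events. A limit called a NOAEL exposure tells the Safety Review Group that no adverse effect was seen in dogs up to that exposure. By the protocol's own account, the dose named as the source of the limits produced vomiting, tremor and unsteady gait.

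That distinction bears on how the rule is read. Section 1.4 asks for particular attention to early signs of tremor and incoordination as exposure nears levels linked preclinically to CNS effects. Someone working from Section 7.4 alone would misplace where that region begins. The provision that "Planned dose levels may be changed based on emerging data" keeps the rule live in principle. Section 3.3 says the data from this study will be used to design later Phase I studies, including multiple ascending dose studies, so a mislabelled margin could be carried forward.

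**Working it through.** No sample-size or power formula applies. The check asks whether the limits reproduce as the NOAEL exposure and, if not, which dog dose they fit.

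**Inputs**

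| Quantity | Cmax (µg/L) | AUC(0-24) (µg·h/L) | Protocol source |
|---|---|---|---|
| PK stopping limit | 634 | 6025 | 7.4 |
| Dog, 5 mg/kg, week 1 | 175 | 860 | 1.4 |
| Dog, 5 mg/kg, week 4 | 238 | 1611 | 1.4 |
| Dog, 20 mg/kg, week 4 | 1682 | 15887 | 1.4 |

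**Step 1: do the limits reproduce as the exposure at the 5 mg/kg NOAEL?** They do not.

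- Against week 4: 634/238 = 2.66 and 6025/1611 = 3.74.
- Against week 1, the time point at which Section 1.4 first attaches the word NOAEL: 634/175 = 3.62 and 6025/860 = 7.01.

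Section 7.4 specifies 4 weeks, so the week-4 ratios are the relevant ones.

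**Step 2: do the limits fit 10 mg/kg?** The 10 mg/kg exposure must be interpolated. Two forms are assumed.

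- Power curve. Since 10 is the geometric mean of 5 and 20, the estimate is the geometric mean of the two exposures: Cmax √(238 × 1682) = 633; AUC √(1611 × 15887) = 5059.
- Straight line. Cmax 238 + (1682 − 238) × 5/15 = 719; AUC 1611 + (15887 − 1611) × 5/15 = 6370.

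The ranges are 633 to 719 for Cmax and 5059 to 6370 for AUC. Both limits lie inside, with Cmax close to the lower end.

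**Step 3: which dose does each limit imply?**

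- Power curve, 5 × (limit/exposure at 5)^(ln 4 / ln(exposure at 20/exposure at 5)): 10.0 mg/kg for Cmax and 11.1 mg/kg for AUC.
- Straight line: 5 + 15 × (634 − 238)/(1682 − 238) = 9.1 mg/kg for Cmax; 5 + 15 × (6025 − 1611)/(15887 − 1611) = 9.6 mg/kg for AUC.

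All four values are near 10 and none is near 5. From 5 to 20 mg/kg, a 4-fold dose step, exposure rises 1682/238 = 7.07-fold (Cmax) and 15887/1611 = 9.86-fold (AUC). That agrees with the more than dose-proportional increase in dogs noted in Section 1.2.

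**Context only.** Section 1.3 reports Cohort 8 (40 mg solution) means of Cmax 612 ng/mL and AUC 4315 ng·h/mL. Against the limits these are 612/634 = 97% and 4315/6025 = 72%; the interval for the human AUC is not stated. They are observed single-dose human means set beside 4-week dog values that the rule applies to predicted means, so they do not show a breach.

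**The case against.** The strongest case against acting is that little is left for the rule to do. It acts on predicted exposure at the next scheduled dose level. Section 1.3 reports 71 volunteers dosed, 63 of them in Cohorts 1 to 8; the other 8 match one further cohort, presumably Cohort 9. That would leave only Cohort 10, which repeats 40 mg, a dose whose tolerability in Cohort 8 was judged acceptable. Section 7.4 names 40 mg solution and 20 mg tablet as the top planned doses, and both have been given. Nothing says that the limits will carry into a later protocol. Safety Review Group members also hold the full protocol, including Sections 1.2 and 1.4. This stands as to scope: the rule does not formally gate Cohort 10, and the link to later studies is a risk rather than a stated plan.

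The interpolation can be challenged too. It rests on two dose points and two assumed curves, and on the power curve the AUC limit is 19% above the 10 mg/kg estimate (6025/5059 = 1.19). It shows compatibility with 10 mg/kg and does not prove it. The contradiction does not depend on it.

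The sponsor may also have chosen the 10 mg/kg exposure deliberately. If so, the NOAEL label is wrong and the choice is unexplained. The other 10 mg/kg figures in the Summary and Sections 1.2 and 3.3 do not help: they are single-dose rat no-effect levels or the dog effect dose itself. Finally, the 5 mg/kg statements are not independent, because the Summary and Section 3.3 repeat the same text. Even so, none of them supports 10 mg/kg as the dog NOAEL.

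**Conclusion.** The concern holds. In the text available, every statement of the repeat-dose dog NOAEL outside Section 7.4 gives 5 mg/kg, and Section 1.2 treats 10 mg/kg as a dose with clinical signs. Section 7.4 is therefore wrong as written, either in the label or in the source dose and its two values.

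The gap to the reported week-4 exposure at 5 mg/kg is 2.66-fold for Cmax and 3.74-fold for AUC(0-24). These ratios use only figures printed in the protocol. The reading that the limits are 10 mg/kg exposures rests on the assumed interpolation, because the 10 mg/kg exposure is not reported.

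The contradiction is certain and its practical reach in this trial is limited. It should still be corrected, because the stated basis of a safety decision threshold conflicts with the protocol's own data. No view is taken on which element is right or what the limit should be.

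**What to change.** Check the dog toxicokinetic report for the dose and time point behind 634 µg/L and 6025 µg·h/L. Then reconcile Section 7.4 with the Protocol Summary and Sections 1.2, 1.4 and 3.3, so that the numerical limits and their stated toxicological basis agree. In Section 7.4, state how the reconciled limits relate to the 5 mg/kg exposures in Section 1.4, and give the reason if they rest on a different dose. Pass the corrected basis to the Safety Review Group for any remaining or later use of the limits.

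The cost is one document check and a correction or amendment to Section 7.4. It needs no extra subjects, samples or procedures.
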